6.1 Ethical Considerations: Informed Consent/Accent and HIPAA Authorization

Each patient will be assigned a random alphanumeric code that will be associated with their survey information. No specific patient identifiers will be recorded along with the survey data. Identifying patient information and research data will be de-identified at the earliest reasonable time after it is received or collected, and a unique study identifier code will be used which does not directly identify the participant. All computers will be password protected and all data will be kept in locked cabinets only accessible by members of the research team. The principal investigator, study monitors, and student researchers will have access to the data. Identifiable data will be destroyed after 1 year and de-identified data will be destroyed after 5 years.

Yale will minimize this risk of breach in confidentiality by (a) removing direct identifiers from stored participant information (e.g. names, medical record number); (b) securing any identifiable data in a separate location and limiting access to only those members of the research team listed on the protocol; (c) limiting access to stored information to only those members of the research team listed on the protocol.

Subject will be consented in a private room by a designated member of the study team listed above. Each subject will be consented in the language appropriate and presented with a consent form, written in that language. All aspects of the study will be discussed with the potential subject including the reason the subject is being asked to participate, the schedule of visits, the study activities that will occur, and the risks and benefits of participation. The subject will then have an opportunity to ask any questions they have. Once all questions have been answered and the subject feels that he/she would like to participate, the designated member of the research team will ask the subject to provide verbal consent. Participants will have time between the explanation of the project and the commencement of the appointment to consider and provide consent to participate. A subject's capacity to provide consent will be evaluated by a member of the consenting staff based on the questions the subject asks about his/her involvement in the study as well as by asking the subject questions pertaining to aspects of the study.

Additional text if applicable:

A verbal explanation will be provided in terms suited to the participant's comprehension of the purposes, procedures, and potential risks of the study and of their rights as research participants.

6.2 Institutional Review Board (IRB) Review

If this study is approved by the IRB protocol modifications, study team updates, reportable events, and unanticipated problems will be reported immediately, if possible, or within 5 days. The study is a prospective study conducted via survey data collection from patients.

6.3 Subject Confidentiality

Data will be collected via handwritten surveys entered the computer, paper files, and via electronic devices like an iPad. The physical files will be stored in locked filing cabinets while electronic data will be stored via laptop computer using encrypted software. The principal investigator, study monitors, and student researchers will have access to the data. Yale will minimize this risk of breach in confidentiality by (a) removing direct identifiers from stored participant information (e.g., names, medical record number); (b) securing any identifiable

data in a separate location and limiting access to only those members of the research team listed on the protocol; (c) limiting access to stored information to only those members of the research team listed on the protocol.

6.4 Deviations/Unanticipated Problems

This protocol presents minimal risks to the subjects and Unanticipated Problems Involving Risks to Subjects or Others (UPIRSOs), including adverse events, are not anticipated. In the unlikely event that such events occur, Reportable Events (which are events that are serious or life-threatening and unanticipated (or anticipated but occurring with a greater frequency than expected) and possibly, probably, or definitely related) or Unanticipated Problems Involving Risks to Subjects or Others that may require a temporary or permanent interruption of study activities will be reported immediately (if possible), followed by a written report within 5 calendar days of the Principal Investigator becoming aware of the event to the IRB (using the appropriate forms from the website) and any appropriate funding and regulatory agencies. The investigator will apprise fellow investigators and study personnel of all UPIRSOs and adverse events that occur during the conduct of this research project via email as they are reviewed by the principal investigator. The protocol's research monitor(s) and regulatory and decision-making bodies will be informed of adverse events within 5 days of the event becoming known to the principal investigator.

6.5 Data Quality Assurance

To ensure good clinical practices are followed, researchers will follow-up with the principal investigator to communicate weekly experiences and are expected to communicate any concerns, protocol deviation, or questions immediately. The principal investigator is responsible for monitoring the data, assuring protocol compliance, and conducting the safety reviews on a monthly basis.

6.6 Study Records

Study records include study surveys, consent forms, and subject medical records.

6.7 Access to Source

Each patient will be assigned a random alphanumeric code that will be associated with their survey information. No specific patient identifiers will be recorded along with the survey data. Identifying patient information and research data will be de-identified at the earliest reasonable time after it is received or collected, and a unique study identifier code will be used which does not directly identify the participant. All computers will be password protected and all data will be kept in locked cabinets only accessible by members of the research team. Collaborators will be provided access to data after obtaining permission from the principal investigator.

6.8 Data or Specimen Storage/Security

Data will be collected via handwritten surveys entered into the computer, paper files, and via electronic devices like an iPad. The physical files will be stored in locked filing cabinets while electronic data will be stored via laptop computer using encrypted software.

6.9 Retention of Records

Identified data will be retained for 1 year and deidentified data will be retained for 5 years. If permission is needed to remove or destroy data, the principal investigator will be to be contacted.

6.10 Study Monitoring

The principal investigator is responsible for monitoring the data, assuring protocol compliance, and conducting the safety reviews on a monthly basis. During the review process the principal investigator will evaluate whether the study should continue unchanged, require modification/amendment, or close to further enrollment.

6.11 Study Modification

The principal investigator, the Institutional Review Board (IRB), or study monitor have the authority to stop or suspend the study or require modifications.

6.12 Study Completion

This study's anticipated completion date for data collection is May 23rd, 2022 – August 08th, 2022, IRB will be contacted via email to provide written confirmation of the study completion.

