CLINICAL STUDY PROTOCOL

Observational Study of Individual or Group Template

Investigating the Impact of a Shared Decision-Making Tool on Patient Attitudes and Behaviors Regarding Treatment for Knee Osteoarthritis

2000032637

Protocol Version

February 18, 2022

Version 1

Confidentiality Statement:

Synopsis

Purpose

The purpose of this study is to determine the impact of a Shared Decision-Making Tool (SDMT), which provides information about osteoarthritis disease progression, on a patient's decision to pursue treatment for knee osteoarthritis.

Primary Objective

The primary objective of this study is to assess the impact of the shared decision-making tool on a patient's decision to seek treatment for knee osteoarthritis.

Secondary Objective

Our secondary objectives include investigating the impact of the SDMT on patient understanding of disease progression as well as patient understanding of the impact of treatment on disease progression. Additional secondary objectives include evaluating the impact of the SDMT on patient behaviors and engagement with treatment modalities.

Study Design

This is a randomized control trial in which participants will be assigned to one of two arms. Patients in the control arm of the study will watch a short video and then receive standard of care counseling with an orthopaedic surgeon. Patients in the treatment arm of the study will watch a short video and then receive standard of care counseling with an orthopaedic surgeon that includes discussion of the SDMT. All patients will complete pre- and post-visit surveys designed to measure the severity of their knee osteoarthritis and their willingness to proceed with different treatment modalities.

All patients who are receiving care for knee osteoarthritis with one of the participating orthopaedic surgeons, and are greater than age 18 and speak English, will be eligible for inclusion in the study. The study will be conducted at Yale-affiliated clinics.

Study Date Range and Duration

Patient responses for this study will be collected between May 23rd, 2022– August 08th, 2022.

Number of Study Sites

- Yale Ortho – New Haven Office
Yale Physician Building [name]
- Yale Ortho – Milford
[name]
- Yale Medicine Multispecialty
[name]

Primary Outcome Variables

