4.1.2 Study Date Range and Duration

Patient responses for this study will be collected between May 23rd, 2022 – August 8th 2022.

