5.1 Study Procedures

Potential subjects will be identified by the PI and participating orthopaedic surgeons. The PI and Sub-I will recruit potential subjects for this study.

Subjects will be consented in a private room by a designated member of the study team. Each subject will be consented in the language appropriate and presented with a consent form, written in that language. All aspects of the study will be discussed with the potential subject including the reason the subject is being asked to participate, the schedule of visits, the study activities that will occur, and the risks and benefits of participation. The subject will then have an opportunity to ask any questions they have. Once all questions have been answered and the subject feels that he/she would like to participate, the designated member of the research team will obtain verbal consent for the study.

A subject's capacity to provide consent will be evaluated by a member of the consenting staff based on the questions the subject asks about his/her involvement in the study as well as by asking the subject questions pertaining to aspects of the study.

Eligible patients who agree to participate and provide verbal informed consent, will be randomized to participate in either the Control Group or Intervention Group. Both groups will complete the PROMIS Computer Adaptive Test and pre-survey as well as watch a short video providing general information about knee OA. The intervention for the intervention group will be the surgeon utilizing the SDMT during the visit. Both the control and intervention group will complete the post-event survey immediately after completing the control or intervention and then 1 month later.

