5.4.6 Handling of Missing Data

Patients who have missing data will be excluded from the analysis.

6 Trial Administration

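### The only dates given end all response collection on 8 August 2022, with no enrolment cut-off, so patients enrolled after about 8 July could not complete the one-month survey

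*Combined protocol and SAP*

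**What the plan says.** The synopsis and section 4.1.2 set one period for survey data: "Patient responses for this study will be collected between May 23rd, 2022 – August 8th 2022". Section 6.12 repeats the range as the end of the study's data collection: the "anticipated completion date for data collection is May 23rd, 2022", continuing to 8 August 2022.

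Section 5.1 says that both arms "will complete the post-event survey immediately after completing the control or intervention and then 1 month later". The table in section 5.4.2 labels the one-month survey a secondary study outcome. The synopsis describes a follow-up of one month, assumes 10-20% attrition, and plans to enrol 200-250 patients around a target of 200. Section 5.4.6 states: "Patients who have missing data will be excluded from the analysis".

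No section gives an enrolment period, a last-enrolment date, or an allowance for one-month surveys after 8 August. Section 6.10 lets the principal investigator close enrolment after a monthly review but attaches no date.

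**The concern.** A one-month survey is a patient response, so it falls under the 8 August end date. The last visit date that leaves a full calendar month is 8 July. Without a stated cut-off, staff could follow the protocol exactly and keep enrolling into August, and those later patients could not supply the one-month outcome within the protocol's dates.

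This gap would come from the schedule and not from patient behaviour. It would be added to the attrition already assumed, and no analysis method can recover a survey that was never collected. The exclusion rule in section 5.4.6 adds a second question, because it does not say whether a missing one-month survey removes a patient from the one-month analysis only or from every analysis.

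**Working it through.** **The plan's own figure.** The upper enrolment figure is the target inflated for 20% attrition: 200 / (1 - 0.20) = 250. For 10% it is 200 / (1 - 0.10) = 222.2, or 223. So 250 covers the stated attrition and leaves nothing for a loss caused by the dates. The lower figure of 200 allows for no loss at all.

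**Share of the window.**
- 23 May to 8 August inclusive: 78 days.
- 23 May to 8 July inclusive: 47 days.
- 9 July to 8 August inclusive: 31 days.
- 31 / 78 = 39.7%. With a 30-day month, 30 / 78 = 38.5%; with a 28-day month, 28 / 78 = 35.9%.

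**Patients, assuming even accrual that runs to 8 August.** Neither part of this assumption is in the documents.

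| | 200 enrolled | 250 enrolled |
|---|---|---|
| Cannot reach one month (x 31/78) | 79 | 99 |
| Can reach one month (x 47/78) | 121 | 151 |
| After 10% attrition (x 0.9) | 108 | 136 |
| After 20% attrition (x 0.8) | 96 | 121 |

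**Precision.** Section 5.4.1 gives power 0.8 but no significance level, allocation ratio or score scale. I assume two-sided 0.05, equal arms and a two-sample t-test, and express the detectable difference d in standard deviations. Approximately, d = (1.960 + 0.842) x sqrt(4 / N); the exact t calculation gives:
- N = 200, no loss: 0.40.
- N = 121, dates alone for 200 enrolled: 0.51.
- N = 180 to 160, attrition alone for 200 enrolled: 0.42 to 0.45.
- N = 136 to 96, dates and attrition together for 200-250 enrolled: 0.48 to 0.58.

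**Power on the plan's own assumptions.** If the 10% difference in section 5.4.1 means 10 points with a standard deviation of 10, power at N = 96 is still above 0.99. That reading cannot be confirmed, because section 5.4.2 scores each item from 1 to 5 and no total scale is defined.

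**Accrual rate if enrolment closed on 8 July.** 47 days is 6.71 weeks, so 200 / 6.71 = 30 and 250 / 6.71 = 37 patients a week. Over the full 78 days (11.14 weeks) the rates are 200 / 11.14 = 18 and 250 / 11.14 = 22.

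**The case against.** The strongest reply is that the documents give no enrolment window. A reader might infer that enrolment runs through the same dates as response collection, so that the schedule itself rules out the outcome for 40% of patients. The text does not support that. The stated range covers responses, and closing enrolment around 8 July would fit every date in the protocol. The 40% is a share of calendar time; it becomes a share of patients only under even accrual to the last day. What remains is that no cut-off is written down.

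A reader might also infer that the primary analysis must shrink. Section 5.4.6 does not say so. Excluding patients analysis by analysis is as natural a reading as excluding them from everything, and section 5.4.2 lists the primary outcome separately from the one-month survey. The effect on the primary analysis therefore depends on how that sentence is read.

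Nor do the documents show that the engagement outcome rests on the one-month form. The survey items are not given, and section 4.2.2 ties engagement to the pre- and post-surveys in general.

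Two further points limit the consequence. The loss should be similar in both arms, so bias between arms is not the main worry. And on one reading of the plan's effect assumptions, power stays very high even at 96 patients. Both stand, and they lower the priority; they do not remove the gap in the dates.

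**Conclusion.** The concern holds as an omission. All response collection ends on 8 August 2022, each patient owes a survey one month after the visit, and nothing stops enrolment after about 8 July or lets collection run later. The exposed period is 36-40% of the window, depending on how a month is counted.

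Under the accrual assumption above, 121-151 patients could reach one month, and 96-136 would remain after the protocol's own attrition, so even 250 enrolled would fall short of 200 with one-month data. The cost is mainly precision on a secondary outcome. It extends to the primary outcome only if section 5.4.6 is applied across all analyses. This is a cheap improvement, not a change that the trial cannot do without.

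**What to change.** In sections 4.1.2 and 6.12, and in the matching synopsis entry, replace the single range with two dates: the last enrolment and the end of one-month survey collection.

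- **Preferred:** keep enrolment open to 8 August and collect one-month surveys to about 8 September plus a short return window. This costs about one more month of survey return. It needs no extra visit, since section 5.3.3 makes the scheduled appointment the only study visit.
- **Alternative:** close enrolment by about 8 July and keep 8 August as the end of collection. This needs 30-37 patients a week in place of 18-22.

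In section 5.4.6, state that a missing one-month survey excludes a patient from the one-month analysis only, and not from the immediate post-visit analysis. This costs one sentence.

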6.13 Funding Source

There is currently no funding request or support for this study.

6.14 Conflict of Interest Policy

There are no conflicts of interest to report.

6.15 Publication Plan

Once the research is complete, there is a plan to submit to peer-reviewed journals for publication along with submission to specialty-related conferences for presentation.

Appendices

Appendix #	Title	Section	Topic

List of Tables
